1.0 INTRODUCTION

Allogeneic hematopoietic stem cell transplantation (HCT) is the only potentially curative therapy available to patients with myelodysplastic syndromes (MDS). Until recently, however, concerns regarding morbidity and mortality of this intensive procedure limited its application in older patients with MDS. The introduction of reduced intensity conditioning (RIC) regimens greatly expanded the utility of HCT in older and sicker patients by reducing the risk of regimen-related toxicity^{1,2}. Although several small studies indicate safety and efficacy of HCT in older patients,^{3,4} there are no large prospective studies evaluating outcomes in patients older than 65 years. The aim of this study is to prospectively examine post-HCT outcomes in CMS beneficiaries with MDS to determine whether these outcomes are similar to those in younger patients where the experience with HCT is more extensive and where HCT is an accepted medical therapy.

2.0 HYPOTHESIS:

The outcome of HCT for MDS and related disorders in ≥ 65 years of age is similar to outcomes in adults 55-64 years of age.

3.0 SPECIFIC AIMS

3.1. To prospectively determine the following outcomes in Medicare beneficiaries who undergo HCT for MDS and related disorders and compare these outcomes with those of non-Medicare beneficiaries, aged 55-64:

- Early (100-day) mortality
- Acute and chronic graft-versus-host disease (GVHD)
- Relapse and progression
- Disease-free survival
- Progression-free survival
- Overall survival

3.2. To prospectively determine whether there are disease- or patient-related factors that predict outcomes of HCT for MDS and related disorders in Medicare beneficiaries, including:

- World Health Organization (WHO) classification
- International Prognostic Scoring System (IPSS) score
- WHO-based Prognostic Scoring System (WPSS)
- Cytopenias
- Cytogenetics
- Primary versus secondary MDS
- Disease duration and prior therapy
- Recipient age
- Performance score
- Sorrow co-morbidity index

3.3. To prospectively evaluate what transplant characteristics are associated with outcomes of HCT for MDS and related disorders in Medicare beneficiaries, including:

- Preparative regimen
- Graft source
- GVHD prophylaxis
- Use of hematopoietic growth factors

3.4. To prospectively evaluate treatment facility characteristics associated with outcomes of HCT for MDS and related disorders in Medicare beneficiaries, including:

- Transplant volume
- Years of operation
- Academic affiliation

This study is Part 1 of a comprehensive evaluation of HCT in Medicare beneficiaries. It will evaluate outcome of allogeneic HCT, with monitoring to ensure that there is not undue early mortality in adults ≥ 65 years of age. The intent was to assemble a high quality data set of 240 patients, whose data will be analyzed to provide information pertinent to design of Part II of the study. In addition it would prospectively evaluate the effect of various disease, patient and treatment facility characteristics related to outcome. The study protocol is amended October 30, 2012 to increase the accrual to provide sufficient power to evaluate the effect of these prognostic factors on outcomes of HCT.

4.0 BACKGROUND:

Myelodysplastic syndromes are a group of clonal hematological disorders characterized by progressive cytopenias and leukemic transformation. More than 15,000 patients are diagnosed with MDS each year in the United States, and 80% of those patients are older than 65 years of age. The median age at diagnosis is 70 years in western countries and incidence increases with increasing age. The incidence is 0.22/100,000 in those <49 years, 4.8/100,000 between the ages of 50 and 70 years and 22.8/100,000 in those older than 70 years⁵.

MDS is classified using several systems. For many years, MDS subtypes were classified by morphology using the French-American-British (FAB) classification; this has now largely been superseded by the WHO classification, which also incorporates cytogenetic abnormalities (5q-). Several prognostic scoring systems are also available. The International Prognostic Scoring System (IPSS) is the most widely accepted. The IPSS uses percentage of blasts, cytogenetic abnormalities and cytopenias to separate patients into 4 different prognostic groups: Low, intermediate-1, intermediate-2 and high risk. Median survivals vary from 0.4 years to 5.7 years for untreated patients with high and low risk disease respectively⁶. More recently, a prognostic system using the WHO classification, transfusion requirement and IPSS cytogenetic risk, the WPSS) is suggested to provide better prognostic

discrimination⁷.

Recently the Food and Drug Administration approved three new drugs for therapy of MDS: azacytidine⁸, decitabine⁹ and lenalidomide¹⁰. Both azacytidine and decitabine are hypomethylating agents while lenalidomide is a thalidomide analogue. The response rates to those drugs range from 30-70%, however none are curative.

The only available therapy with the potential to cure MDS is HCT and HCT is the treatment of choice for younger patients¹¹. Prior to the introduction of RIC regimens, regimen-related morbidity and mortality limited the utility of HCT in older patients and in those with significant co-morbidities. RIC regimens now allow HCT to be offered more safely to those patients but use of HCT in the older population still remains limited. This was evident in a recent study by the CIBMTR where only 10% of patients who underwent RIC HCT were older than 65 years. In that study, age had no significant impact on outcome in multivariate analysis in a cohort of patients between 40 and 70 years.¹² The 100 day mortality rate was about 20% and the 2 year probability of survival was about 40%.

There are multiple reasons that older patients do not undergo transplantation. Older patients may have co-morbidities that compromise their ability to tolerate an intensive therapy like HCT. Some oncologists are reluctant to refer older patients for HCT, even if there are no clinical contraindications, because of perceived worse outcomes in older patients. Some transplant centers have arbitrary upper age limits for HCT candidates. Finally, some third party payers will not cover HCT in older patients until there is transformation to acute leukemia. Until recently, coverage of HCT for MDS by the US Centers for Medicare and Medicaid Services (CMS) depended on local coverage determinations¹³. CMS is the primary health insurer for most US adults 65 years of age or older. Recently, CMS made a National Coverage Determination (NCD) regarding MDS, indicating that data regarding efficacy in a CMS beneficiary population were currently insufficient but that coverage would be provided for patients enrolled in a clinical study appropriately designed to generate data necessary to make a determination about efficacy and effectiveness. This decision acknowledged that “the available evidence suggests that allogeneic HSCT for MDS is reasonable and necessary under §1862(a) (1) (E) of the Social Security Act through Coverage with Evidence Development (CED).”

The aim of this study is to prospectively examine post-HCT outcomes in CMS beneficiaries with MDS to determine whether these outcomes are similar to younger patients where the experience with HCT is more extensive and where HCT is an accepted medical therapy. The study will also evaluate patient, disease and treatment factors which might modify transplant outcomes. The objectives and methods of the study comply with the CMS-specified requirement that a “clinical study seeking Medicare payment ... pursuant to Coverage with Evidence Development (CED) must address one or more aspects” of three questions outlined in its Decision Memo (CAG-00415N). The analyses in this Study Plan are for Part 1 of this evaluation and will directly address questions 2 and 3 in that Memo and will

provide data to plan Part 2 of the evaluation, a study directly addressing question 1 in that Memo, which will compare outcomes after HCT to outcomes with non-HCT therapy.

5.0 STUDY POPULATION:

Eligible patients are persons ≥ 65 years old (or < 65 years of age and a CMS beneficiary) with myelodysplastic syndromes and related disorders, including chronic myelomonocyte leukemia (CMML), who are eligible to receive an allogeneic HCT from either an HLA-identical sibling or unrelated donor in a US transplant center and who agree to (sign Informed Consent; Appendix A) submission of comprehensive clinical data on their pre- and post-transplant clinical status and outcomes to the Center for International Blood and Marrow Transplant Research (CIBMTR). Eligibility for HCT will be according to local institutional practices. Patients younger than 65 years of age who are CMS beneficiaries are included but will be analyzed separately. The object is to capture data on the broad range of patients in whom the therapy is used; there is no exclusion for race, gender or prior therapy.

6.0 OUTCOMES:

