6.2. Secondary outcomes

6.2.1. Acute GVHD: Occurrence of grade II, III and/or IV skin, gastrointestinal or liver abnormalities fulfilling the IBMTR criteria for acute GVHD.

6.2.2. Chronic GVHD: Occurrence of symptoms in any organ system fulfilling the criteria of chronic GVHD.

6.2.3. Relapse: disease recurrence or persistent disease for patients not in CR at transplant. Those who survive without recurrence or persistent disease are censored at the date of last contact.

6.2.4. Progression: increase in marrow blasts to $> 20\%$; patients without progression are censored at time of most recent marrow examination.

6.2.5. Disease-free survival: survival without death or relapse. Those who survive without recurrent or persistent disease are censored at the date of last

contact.

6.2.6. Progression-free survival: survival without increase in marrow blasts to >20%; patients without progression are censored at time of most recent marrow examination.

6.2.7. Overall survival: Surviving patients are censored at the date of last contact.

7.0 DATA COLLECTION:

All data necessary for this study will be collected using the existing mechanisms of the CIBMTR under, operating under the “NMDP and CIBMTR Protocol for a Research Database for Hematopoietic Stem cell Transplantation and marrow Toxic Injuries”, version 6.0, (NCT01166009) (Appendix A). The Informed Consent for this protocol is also found in Appendix A. These data collection mechanisms support the reporting required for the Stem Cell Therapeutic Outcomes Database (SCTOD), and the research endeavors of the CIBMTR. Existing data instruments and procedure manuals can be found at www.cibmtr.org/DataManagement. Registration of patients and submission of data will follow standard CIBMTR procedures.

8.0 STUDY DESIGN:

This study initially had a target accrual of 240 patients older than age 65 for the 100 day mortality primary endpoint. Sample sizes were based on an inferiority test of the hypothesis that the 100 day mortality rate in the ≥ 65 year old cohort is higher than 20%, the approximate 100-day mortality rate in a 55-64 year old cohort¹². The study was designed to have approximately 80% power to detect a 6.5 % or greater increase in 100 day mortality rate in the ≥ 65 year old cohort. Table 1 below shows the power of the test for various 100 day mortality rates.

Table 1.	
True 100 day mortality rates	Power
0.21	10%
0.22	20%
0.23	32%
0.24	46%
0.25	60%
0.26	73%
0.27	83%
0.28	90%
0.29	94%

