At each of the four evaluations points, we will prepare descriptive tables of the covariates. Kaplan-Meier estimates of mortality and disease free survival will be

constructed for the entire cohort and by sub-groups defined by the fixed covariates such as IPSS score. Cumulative incidence curves will be constructed to estimate acute GVHD incidence, relapse progression rates. These analyses will be conducted when 60, 120, 180 or 240 patients have at least 100 days of potential follow-up. As they are descriptive in nature, no p-values are computed until the entire cohort has been observed.

When accrual of the first 240 patients is complete and all patients have been followed for at least 100 days, the association between outcomes and the variables listed in Section 3.0 will be examined in either a logistic regression model or a Cox proportional hazards model depending on the outcome of interest. Forward stepwise model selection techniques will be used in this approach. These analyses will include a cohort of patients ages 55-64 years transplanted for MDS and related disorders in the same centers as the CMS beneficiaries included in this analysis.

After accrual is complete, follow-up of this cohort will continue, through standard CIBMTR mechanisms, after completion of these analyses. Evaluation of all secondary endpoints will be repeated when all patients have been followed for a minimum of two years.

Prognostic factors in patients age 65 and older

Another objective of this study is to determine the prognostic value of patient and disease factors upon outcomes of HCT in patients age 65 and older. After evaluating the demographics of the first 180 patients age ≥ 65 accrued to the protocol, several prognostic factors of interest (sections 3.2 and 3.3) are expected to require larger numbers of patients to achieve adequate power to detect meaningful differences in outcomes for patients in this cohort.

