This study will be performed through the CIBMTR, which has performed hundreds of similar analyses over its >30 year history. The CIBMTR is a clinical research program which receives HCT outcomes data from a network of more than 450 transplant centers worldwide. Data are collected and analyzed by the Statistical Center, located at the Medical College of Wisconsin in Milwaukee, WI, and the National Marrow Donor Program located in Minneapolis, MN. The CIBMTR database includes information on about 330,000 transplant recipients and receives information on about 15,000 new transplants annually. CIBMTR data and statistical and scientific expertise have resulted in hundreds of peer-reviewed publications (www.cibmtr.org/ReferenceCenter/PubList/index.html).

As of December 2007, all United States transplant centers are required to report data on their related and unrelated donor transplants to the CIBMTR; participation of non-U.S. centers is voluntary. Computerized checks for errors, review of submitted data by physicians and on-site audits of participating centers are used to monitor the quality of the data. The CIBMTR collects data on two levels. All centers register basic data (Pre- Transplant Essential Data) for all patients. Centers provide comprehensive data (Report Forms) for a subset of registered patients. Patients are selected for comprehensive data reporting using a randomization program that weights cases for selection in order to provide adequate numbers of cases for current and future studies and to ensure adequate representation of all transplant types and indications. The selection program is modified as needed to select cases for specific studies such as the one described in this protocol. CIBMTR centers are asked to provide follow-up on all patients for as long as they are able to maintain contact. Completeness rates for one and two year survival data are >95%. These data sets have been used to conduct numerous studies of transplant outcomes, including studies of conditioning regimens. The most recent versions of the CIBMTR study forms can be found at http://www.cibmtr.org/DATA/Data_Mgmt_Forms/index.html.

Additionally, we have assembled a team of HCT and MDS experts to guide development, implementation and completion of this study. Biosketches are included in Appendix B.

C. All participating centers will be NMDP and/or FACT accredited. See list in Appendix

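### The index group and the 55-64 comparator are defined inconsistently across Sections 2.0, 3.1, 5.0, 8.0 and 9.13, and the comparator is not held to the Section 5.0 donor types or to a calendar period

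*Protocol*

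**What the plan says.** The protocol describes the age contrast in several places.

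- **Section 2.0 (hypothesis):** the outcome "in ≥ 65 years of age is similar to outcomes in adults 55-64 years of age". Age alone defines both groups.
- **Section 3.1 (aims):** outcomes are determined in Medicare beneficiaries, with no age stated, and the plan is to "compare these outcomes with those of non-Medicare beneficiaries, aged 55-64".
- **Section 5.0 (population):** anyone 65 or older is eligible, as is anyone younger who is a CMS beneficiary. The transplant must be an "allogeneic HCT from either an HLA-identical sibling or unrelated donor in a US transplant center". It adds: "Patients younger than 65 years of age who are CMS beneficiaries are included but will be analyzed separately".
- **Section 8.0 (powered test):** a one-sample test that 100-day mortality in the older cohort is "higher than 20%, the approximate 100-day mortality rate in a 55-64 year old cohort".
- **Section 8.0 (regressions after the first 240 patients):** the models bring in "a cohort of patients ages 55-64 years transplanted for MDS and related disorders in the same centers as the CMS beneficiaries" included in the analysis. No insurance, donor or calendar condition is attached.
- **Section 8.0 (text before Table 2):** the original accrual is described as powered for 55-64 against 65 and older.
- **Section 9.12:** CMS beneficiary status is listed among the eligibility criteria.
- **Section 9.13:** beneficiaries are split at 64/65, and this split is said to allow comparison.

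**The concern.** The study rests on a claim of similarity. Section 6.1.1 justifies transplant at 65 and older by outcomes thought to match those at 55-64, provided the non-age eligibility criteria are alike. The comparison can carry that claim only if a patient's group is fixed before the data are seen and if the two groups differ mainly in age.

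Neither condition is secured. The sections assign the same patient to different groups. The Section 8.0 comparator is not required to meet the donor limits that Section 5.0 sets for enrolled patients, nor to come from the same years. The analyst would have to choose among definitions, possibly after results are known, and the choice can move the estimated age effect.

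At stake are the Section 2.0 hypothesis, every outcome in Aim 3.1 and the Section 8.0 regressions that include the 55-64 cohort.

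**Working it through.** **1. Place two patients under each section.**

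| Section | Age 60, CMS beneficiary | Age 67, not on Medicare |
|---|---|---|
| 2.0 | comparator | index |
| 3.1 | index (no age limit stated) | neither |
| 5.0 | enrolled, analysed apart: neither | index |
| 8.0, regressions | fits the comparator wording | index by age, but not one of the CMS beneficiaries named there |
| 9.13 | younger beneficiary group | neither |

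The first patient takes every possible role. The second is index or outside the comparison.

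**2. Compare eligibility item by item: Section 5.0 against the Section 8.0 comparator.**

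- Disease: matched (MDS and related disorders).
- Center: matched (same centers).
- Donor type: limited in 5.0, not limited in 8.0.
- Insurance: addressed in 3.1, silent in 8.0.
- Calendar period: index patients come from the accrual period; none is stated for the comparator.

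The open items matter because of the data source. The research database protocol in Appendix A admits any related or unrelated donor and cord blood (its Section 2.1), and its component databases date from 1972 and 1989 (its Section 1.3). Section 9.3 of the study protocol itself counts an earlier era as a limitation of existing data.

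**3. Ask whether adjustment would repair this.** Sections 3.2 to 3.4 and 8.1 list the candidate covariates. Neither CMS status nor year of transplant appears. Donor match has three levels (matched sibling, 8/8 unrelated, 7/8 unrelated) and stem cell source has two (marrow, peripheral blood), so a comparator with another donor type or with cord blood has no level to occupy.

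**4. Check whether the powered test is affected.** Inputs from Section 8.0: n = 240, null rate p0 = 0.20, one-sided. The significance level is not stated; one-sided 0.05 reproduces Table 1.

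Power = Φ[(p − p0 − 1.645·√(p0(1 − p0)/n)) / √(p(1 − p)/n)]

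√(0.20 × 0.80/240) = 0.0258, so the critical rate is 0.20 + 1.645 × 0.0258 = 0.2425.

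| True rate | 0.21 | 0.22 | 0.23 | 0.24 | 0.25 | 0.26 | 0.27 | 0.28 | 0.29 |
|---|---|---|---|---|---|---|---|---|---|
| Table 1, % | 10 | 20 | 32 | 46 | 60 | 73 | 83 | 90 | 94 |
| Recomputed, % | 10.8 | 20.0 | 32.3 | 46.4 | 60.6 | 73.2 | 83.2 | 90.2 | 94.8 |

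At 0.265: √(0.265 × 0.735/240) = 0.0285, and Φ[(0.265 − 0.2425)/0.0285] gives 78.5%, against the stated figure of about 80%. Table 1 is thus a one-sample calculation. No 55-64 cohort enters it, so the make-up of that cohort cannot change it.

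**5. Work out the direction of bias.** Suppose, as an assumption, that beneficiaries under 65 have higher early mortality. Under the Section 8.0 wording they can sit in the comparator, raise its rate and shrink the age difference. Under the literal Aim 3.1 wording they sit in the index group, raise its rate and widen the difference. The sign depends on the section followed.

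**6. Try to size it.** If a share f of the comparator has mortality m instead of 20%, its rate becomes 0.20 + f(m − 0.20). The documents give neither f nor m.

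**The case against.** The strongest reply is that the sections can be read together. Sections 2.0 and 6.1.1 give the ages, 3.1 makes the comparator non-Medicare, and 5.0 sets younger beneficiaries apart. Combined, these yield 65 and older against non-Medicare 55-64, with younger beneficiaries reported separately. Section 8.0 names its 55-64 cohort beside the CMS beneficiaries, and it does not say that all patients of that age are taken. This reading is plausible and is close to the fix below. But no section states it, and 9.12 and 9.13 do not fit it.

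It can also be said that the donor levels in 8.1.3 imply the Section 5.0 donor types, and that comorbidity and performance status are candidate covariates, so some imbalance would be adjusted away. Both points hold in part. An implied level is not a selection rule, stepwise selection need not retain a covariate, and period and insurance status stay unadjusted. Extraction details often belong in a statistical analysis plan, but such a plan could only choose between protocol sections that disagree.

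Three stronger readings are tempting, and the documents do not support them.

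- **That the design's ability to detect 6.5 points is eroded.** That figure belongs to the test against a fixed 20%.
- **That the comparison is biased toward similarity, by some number of points.** The direction varies with the section followed, and any magnitude would rest on a share and an excess mortality that the protocol does not supply.
- **That the comparator is a distorted sample.** Section 9.5 does describe choosing patients for comprehensive forms "using a randomization program that weights cases for selection", but it goes on to say that the program is modified for studies such as this one.

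**Conclusion.** The inconsistency is in the text and should be removed before the comparison is made. The index and comparator groups differ among Sections 2.0, 3.1, 5.0, 8.0 and 9.13. The Section 8.0 comparator is matched on disease and center but not on donor type or calendar period. The listed covariates include neither CMS status nor transplant year.

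The consequence is possible bias in the Aim 3.1 comparison and in the Section 8.0 regressions. No bias has been shown, and neither its sign nor its size follows from the documents. Any bias would require the unmatched patients to differ in risk from the rest, which is an assumption. Table 1, the 240 patients and the one-sample test against 20% stand as they are; reproducing Table 1 relies on a one-sided 0.05 level inferred from its entries.

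**What to change.** Put one definition in Sections 2.0, 3.1, 8.0 and 9.13, and bring the eligibility summary in 9.12 into line with it.

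- **Index group:** patients aged 65 and older who meet Section 5.0.
- **Comparator:** non-CMS patients aged 55-64 who meet the same disease and donor criteria, transplanted at the same centers during the study accrual period.
- **CMS beneficiaries under 65:** in neither group, reported separately, as Section 5.0 already says.

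This takes wording changes and extraction filters. The comparator cohort becomes slightly smaller. The powered test and its sample size do not change.

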Based on an 80% power with an assumption of a 25% 100 day mortality in the most favorable group and a delta as indicated, the number of patients needed for each of the analyses is listed below in Table 2. The anticipated accrual for Part I was based on power calculations for a primary outcome of 100 day survival after HCT in patients 55-64 compared to 65 and older. Based upon the distribution of age (65-69 vs. 70 and over), performance score, HCT Comorbidity index¹⁴, IPSS score, and disease status in the first 180 patients enrolled, we anticipate that 700 patients will be required to complete an analysis of prognostic factors for early outcome in patients 65 and older.

Table 2: Number of patients required to test differences in 100 day mortality with 80% power for specified prognostic factors

Prognostic Factor	Number of Patients based on expected difference		
	delta =0.1	delta =0.15	delta =0.2
Age			
<70	580	246	130
≥70	183	78	41
Total	763	324	171
HCT-CI (Sorrer, et al)			
0-2	294	118	59
≥3	222	89	45
Total	516	207	104
Secondary MDS			
No	649	265	133
Yes	163	67	34
Total	812	332	167
Cytogenetics			
Good/Intermediate	376	152	76
Poor	194	79	40
Estimated Unknown/missing/not done	78	32	16
Total	648	263	132
IPSS			
Low.int-1	311	125	62
Intermediate-2/high	214	87	43
Evaluable patients	525	202	105

The above sample size calculations for prognostic factors are based on the estimated frequencies of these potential risk factors using the data accrued in the first 180 patients and a binary response of alive or dead at 100 days. The final analysis of these factors will be performed in a logistic regression model for 100 day survival or a Cox regression model for other events in the cohort of patients age 65 and older.

The distribution of relevant prognostic factors shown in sections 3.2 and 3.3, and in the power calculations shown in Table 2 will be reviewed after accrual of 500 patients age 65 and over. Adjustments will be made to the final accrual projections at that time.

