8.1. Variables to be analyzed for their association with primary and secondary outcomes

8.1.1. Patient related:

- Age: in five year increments (or appropriate cutpoint based on data analysis)
- Gender: male vs. female
- Race: Caucasian vs non-Caucasian
- Karnofsky performance status: <80% vs. ≥80%
- Sorror co-morbidity Index

8.1.2. Disease related:

- WHO Disease classification at diagnosis and just prior to HCT
- FAB classification
- Pretransplant WBC and untransfused platelet count and hemoglobin concentration
- IPSS score immediately prior to transplantation
- WPSS score immediately prior to transplantation
- Cytogenetics
- Primary versus secondary MDS
- Time from diagnosis to transplant: <1 year vs. ≥ 1 year (or more appropriate cutpoint based on data analysis)
- Agents used for prior therapy

8.1.3. Transplant related:

- Conditioning regimen: more versus less intensive; specific regimens to be evaluated if numbers of patients sufficient
- Donor age
- Donor-recipient CMV status: -/- vs. -/+ vs. +/- vs. +/+
- Donor-recipient HLA match: HLA matched sibling vs. 8/8 locus (HLA- A, B, C, DRB1) matched unrelated donor vs. 7/8 locus matched unrelated donor
- Stem cell source: bone marrow vs. peripheral blood
- GVHD prophylaxis: Cyclosporine or Tacrolimus + Methotrexate vs. ex vivo T- cell depletion vs. other
- Donor-recipient gender match: male-male vs. male-female vs. female-male vs. female-female
- Transplant center characteristics: transplant volume, years of operation, academic affiliation

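### Centre-level factors in Aim 3.4 go into logistic or Cox models with stepwise selection and no stated centre effect; if outcomes vary between centres, their standard errors will be too small

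*Protocol*

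**What the plan says.** Section 3.4 states the aim: "To prospectively evaluate treatment facility characteristics associated with outcomes of HCT for MDS and related disorders in Medicare beneficiaries". Section 8.1.3 lists the factors among the variables to be related to the primary and secondary outcomes: "Transplant center characteristics: transplant volume, years of operation, academic affiliation".

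Section 8.0 gives the method. Once the first 240 patients have 100 days of follow-up, "the variables listed in Section 3.0 will be examined in either a logistic regression model or a Cox proportional hazards model", depending on the outcome, and "Forward stepwise model selection techniques will be used in this approach". These analyses also take in a cohort aged 55-64 from the same centres; its size is not stated. Because Aim 3.4 is part of Section 3.0, the facility factors fall under this rule.

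For the enlarged accrual of 700, Section 8.0 repeats the model classes: "The final analysis of these factors will be performed in a logistic regression model for 100 day survival or a Cox regression model". It ties the enlargement to two other groups of factors: "several prognostic factors of interest (sections 3.2 and 3.3) are expected to require larger numbers of patients". Table 2 has no facility row. The closing paragraph of Section 3.0 is broader: it mentions facility characteristics and then says that accrual was raised to give enough power for these prognostic factors.

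Nowhere does the protocol mention a centre random effect, frailty, robust variance or stratification by centre. It also does not say that patients are treated as independent, or which variance estimator will be used.

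**The concern.** Two patients at the same centre share the same volume, age of programme and affiliation. The evidence on such a factor therefore comes mainly from differences between centres, and the number of centres limits it. A model with one row per patient and no centre term counts every patient as separate evidence on the factor.

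The protocol gives reasons to expect outcomes to differ between centres. Eligibility follows local institutional practice (Section 5.0), some centres set their own upper age limits (Section 4.0), and centres choose the treatment (master protocol, Section 1.3). Aim 3.4 itself presumes that facilities may matter.

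At stake is the reliability of the Aim 3.4 results. Standard errors that are too small overstate significance and give intervals that are too narrow. Where selection rests on p-values, they also let centre-level terms into the model too easily. The point estimates are not the issue.

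**Working it through.** **The plan's own figure.** No stated figure covers facility effects. Table 1 concerns the primary test, and reproducing it shows what that test uses. Inputs from Section 8.0: N = 240 and null rate p0 = 0.20. Alpha is not stated; one-sided 5% is inferred because it fits.

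Power = Φ{[p1 − p0 − 1.645·√(p0(1−p0)/N)] / √(p1(1−p1)/N)}

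At p1 = 0.25: (0.05 − 1.645 × 0.02582) / 0.02795 = 0.27, so power is 60.6% (stated 60%). Over true rates 0.21 to 0.29 the formula gives 10.8, 20.0, 32.3, 46.4, 60.6, 73.2, 83.2, 90.2 and 94.8%, against 10, 20, 32, 46, 60, 73, 83, 90 and 94% in the table. The test compares one proportion with a fixed 20% and uses no facility covariate.

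**Inputs for the facility factors.**
- Patients: 240 (the analysis of all Section 3.0 variables) or 700 (the enlarged accrual), both from Section 8.0.
- Participating centres: not given in the available text; assumed 40 to 100.
- ICC after covariate adjustment: not given; assumed 0.01 to 0.05.
- Coefficient of variation (CV) of centre size: not given; assumed 0 to 1.

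**Formulas.** With m = patients / centres, for a covariate constant within a centre:
- design effect DE = 1 + [(1 + CV²)·m − 1]·ICC
- true SE / patient-level SE = √DE
- true size of a nominal two-sided 5% test = 2·[1 − Φ(1.96/√DE)]

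Largest case: 700 patients in 40 centres gives m = 17.5. With CV 1 and ICC 0.05, DE = 1 + (35 − 1) × 0.05 = 2.70, √DE = 1.64, and size = 2·[1 − Φ(1.19)] = 23%.

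Smallest case: 240 patients in 100 centres gives m = 2.4. With CV 0 and ICC 0.01, DE = 1 + 1.4 × 0.01 = 1.01 and size = 5.2%.

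| Patients | Centres | m | DE | SE ratio | True size |
|---|---|---|---|---|---|
| 240 | 40 | 6.0 | 1.05-1.55 | 1.02-1.24 | 5.6-11.5% |
| 240 | 100 | 2.4 | 1.01-1.19 | 1.01-1.09 | 5.2-7.2% |
| 700 | 40 | 17.5 | 1.17-2.70 | 1.08-1.64 | 6.9-23% |
| 700 | 100 | 7.0 | 1.06-1.65 | 1.03-1.28 | 5.7-12.7% |

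Each range runs from ICC 0.01 with CV 0 to ICC 0.05 with CV 1. The rows for 240 count only the older cohort. Adding patients aged 55-64 from the same centres would enlarge the clusters.

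**Check by simulation.** Patient-level logistic models were fitted to null data: 700 patients, 25% mortality, size CV 1, 50 or 80 centres, 800 runs per setting. The ICC here is on the latent (logit) scale, so it does not correspond one to one with the ICC in the formula.

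| Latent ICC | Size, patient-level SE | Size, cluster-robust SE |
|---|---|---|
| 0 | 5.4-6.8% | 6.8-7.6% |
| 0.02 | 7.8-8.8% | 6.8-7.4% |
| 0.05 | 12-14% | 6.9-7.9% |
| 0.10 | 18-23% | 7.5-9.0% |

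The direction agrees with the formula. Cluster-robust errors remove most of the inflation at higher ICC but stay above 5%. These figures are for a single test of one factor in a logistic model. Cox models, the stepwise procedure, and the random-intercept and frailty models were not simulated.

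**The case against.** The strongest reply is that the protocol is silent here rather than wrong. Naming a logistic or Cox model does not exclude a random effect, a frailty or a robust variance, and such detail is commonly left to a statistical analysis plan, which is not shown. A reader might infer that the protocol prescribes models treating patients as independent, so that the standard errors are certainly too small. The text does not say that, and the point has to be put conditionally. What remains is that Section 9.8 calls this document the written study plan, and Section 8.0 already fixes the model class and selection method. It treats centre-level factors exactly like patient-level ones. Followed as written, with nothing added, it gives standard errors that are too small whenever outcomes vary between centres.

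The second reply concerns size. The number of centres, the ICC and the size variation are all assumed. Performance status, comorbidity, IPSS, conditioning and donor match are candidate covariates (Section 8.1), so only the residual ICC counts. The analysis covering all Section 3.0 variables is attached to 240 patients plus the younger cohort, and the enlargement to 700 is tied to Sections 3.2 and 3.3. All of this stands. With 240 patients in many centres the effect is trivial, which is why both sample sizes are shown.

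Two further inferences are not supported. A reader might think that a matched design is being wasted, since the comparators come from the same centres. But Section 8.0 describes no matching, and because age group varies within centres, the formula above does not apply to that contrast. A reader might also think that individual facilities will be judged favourably or unfavourably. Aim 3.4 concerns associations with three characteristics, and nothing in the protocol ranks centres.

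**Conclusion.** The point holds as a cheap improvement to a secondary aim. The protocol names only logistic or Cox models with forward stepwise selection for factors that are constant within a centre, and provides for no centre effect. If residual outcomes vary between centres and nothing is added, a nominal 5% test of a facility factor has a true size of about 5-12% with 240 patients and 6-23% with 700. This rests on 40 to 100 centres, ICC 0.01 to 0.05 and size CV 0 to 1, none of which the protocol gives. At the low end the inflation is negligible; at the high end the true standard error is 1.64 times the patient-level one. It would be wrong to conclude that the primary result is compromised, because the test against 20% uses none of these covariates.

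**What to change.** Add to Section 8.0 that, for transplant volume, years of operation and academic affiliation, the logistic model will include a random centre intercept and the Cox model a shared centre frailty. Use cluster-robust standard errors as a sensitivity analysis only, since in the simulation they still gave 6.8-9.0% at latent ICC 0.02 to 0.10. State also that these models will not be stratified on centre: a factor with one value per centre has no variation within strata, so its effect could not be estimated.

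The change needs a sentence or two and routine software, and no new data or patients. The price is wider intervals for facility effects. No stated sample size or power figure changes.
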